Participants who were initially enrolled to receive placebo (Groups 6, 8 and 10), will be offered a 2-dose (28-day interval) Ad26.COV2.S vaccination regimen at the $5x10^{10}$ vp dose level. In October 2020, the study was temporarily paused because one of the pausing rules was met in study COV3001. When the pause was lifted, most of the participants in Groups 7-8 had missed their visit window for Vaccination 2 (Visit 4), rendering the intent of the 28-day vaccination interval in these groups futile. The goal in offering 2 doses of study vaccine to those participants who initially received placebo in this study is to recreate this 28-day vaccination interval, and to restore the objectives associated with this interval. The original 28-day interval target group was 75 participants. Hence the total number of placebo recipients from Groups 6, 8 and 10 (target n=75) is intended to fulfill the original target enrollment for Group 7.

With the implementation of Amendment 5, all adult participants will be unblinded to the primary vaccination regimen, and adults who received placebo in the primary vaccine regimen will receive a 2-dose active Ad26.COV2.S vaccine regimen at a 28-day interval and at a dose level of $5x10^{10}$ vp, in an open-label manner. Per group, approximately one third of participants will be 65 years and older.

Adult participants who received the active vaccine in the primary vaccine regimen will be followed up for 12 months after vaccination 2; adult participants who received placebo in the primary vaccine regimen will be followed up for 6 months after receipt of the unblinded vaccination 1 (ie, receipt of the first active vaccine following unblinding).

Groups 1-6

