2.1. Study Rationale

Detailed information about the rationale for the selected doses can be found in Section 4.3 Justification for Dose.

Adults

In this study, safety and immunogenicity responses following 2-dose $(5x10^{10} \text{ vp}, 2.5x10^{10} \text{ vp}, 1.25x10^{10} \text{ vp})$ and single-dose $(5x10^{10} \text{ vp}, 1x10^{11} \text{ vp})$ primary vaccination regimens will be assessed in adults aged 18 to 55 years inclusive, and adults in good or stable health aged 65 years and older, to investigate dose sparing measures resulting in an increase of the number of vaccine doses available in a pandemic context. Safety and immunogenicity of 28-, 56-, and 84-day vaccination intervals for the 2-dose regimen $(5x10^{10} \text{ vp})$ will also be assessed to gather insight on the possible compression and delay of the vaccination schedule, as this may be of interest in an emergency use setting.

The $5x10^{10}$ vp dose level is administered in the Phase 3 efficacy studies VAC31518COV3001 (1-dose regimen) and VAC31518COV3009 (2-dose regimen).

In addition, an assessment of the immunogenicity of the 1.25×10^{10} vp Ad26.COV2.S dose level that is representative of the vaccine titer at the end of the foreseen shelf-life for the 5×10^{10} vp dose level in the context of emergency use with storage at 2-8 °C will be done. By lowering the dose level (ie, to 2.5×10^{10} vp and 1.25×10^{10} vp), there will also be a potential to immunobridge to a lower dose level regimen, should the efficacy study (VAC31518COV3001) provide evidence of an immune correlate of protection.

And finally, the anamnestic response after 7 days following a low-dose antigen presentation (1.25x10¹⁰ vp Ad26.COV2.S) as a surrogate of antigen exposure upon SARS-CoV-2 infection,

after the primary 2-dose or single-dose vaccination regimens, will be assessed in adult Groups 1-5, 7 and 9.

Adolescents

Available platform data, as well as safety data from the VAC31518COV1001 study, (see Section 2.2 and Section 2.3.1) support initiating evaluation of Ad26.COV2.S in adolescents aged 12 to 17 years, inclusive. In order to generate data in adolescents that will allow the use of a vaccine to prevent COVID-19 in this age group, the safety and immunogenicity responses following primary vaccination regimens will also be assessed in adolescents aged 12 to 17 years, inclusive.

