400 participants (75 participants per active vaccine group, 25 in the placebo group) will be randomized in parallel in a 3:3:3:3:1 ratio to 1 of 6 vaccination groups. Participants will receive a 2-dose (56-day interval, Groups 1-3) vaccination regimen at different dose levels (5×10^{10} vp, 2.5×10^{10} vp, and 1.25×10^{10} vp) or single-dose vaccination regimen (Groups 4-5) at different dose levels (1×10^{11} vp, 5×10^{10} vp), or placebo (Group 6). For blinding purposes, participants in the single-dose groups (Groups 4-5) will receive a placebo vaccination on Day 57. Additional exploratory cellular immunogenicity evaluations (PBMC) will be performed in a subset of participants (21/group in Groups 1-5, 7 in Group 6; at selected sites). Participants in Group 6 who received 2-doses of placebo in the primary vaccine regimen will receive 2 doses of active vaccine at a single dose level of 5×10^{10} vp, at a 28-day interval.

Groups 7-8

75 participants (50 participants in the active vaccine group, 25 in the placebo group) will be randomized in parallel in a 2:1 ratio, to 1 of 2 vaccination groups. Participants will receive a 2 dose (28-day interval, Groups 7^a) vaccination regimen at a 5×10^{10} vp dose level or placebo (Group 8). Participants in Group 8 who received 2-doses of placebo in the primary vaccine regimen will receive 2 doses of active vaccine at a single dose level of 5×10^{10} vp, at a 28-day interval.

-

^a Group 7 and 8: only 2 subjects (one in each group) are vaccinated at a 28-day interval, due to a study pause

Groups 9-10

75 participants (50 participants in the active vaccine group, 25 in the placebo group) will be randomized in parallel in a 2:1 ratio, to 1 of 2 vaccination groups. Participants will receive a 2 dose (84-day interval, Group 9) vaccination regimen at a 5×10^{10} vp dose level or placebo (Group 10). Participants in Group 10 who received 2-doses of placebo in the primary vaccine regimen will receive 2 doses of active vaccine at a single dose level of 5×10^{10} vp, at a 28-day interval.

The vaccination schedules are presented in Table 2.

Table 2: Vaccination Schedules Adults

Adults ≥18 to ≤55 Years and ≥65 Years

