4. POPULATIONS (ANALYSIS SETS) FOR ANALYSIS

For vaccine studies, study intervention assignment will follow the as treated principle: all analyses (including safety, immunogenicity and efficacy analyses) will be analyzed by the actually received vaccine.

Population	Description
All screened participants (ALL)	The “all screened participants” set includes all participants that were screened, regardless of whether they were enrolled and/or randomized.
All randomized participants (ALL RANDOMIZED)	The “all randomized participants” set includes all participants that were randomized to one of the treatment groups.
Full Analyses Set (FAS)	The full analysis set will include all participants with at least one vaccine administration documented.
Per Protocol Immunogenicity Set (PPI)	The per protocol immunogenicity population will include all randomized and vaccinated participants for whom immunogenicity data are available. Samples taken after a participant meets the criteria for a major protocol deviation expected to impact the immunogenicity outcomes will be excluded from the PPI analysis. In addition, samples obtained after missed vaccinations or participants with natural infection occurring after screening (if applicable) will be excluded from the analysis set. SARS-CoV-2 infection is defined as a positive PCR test or positive N-serology.

Two additional analysis sets are defined in Appendix 2 : PPI modified and FAS modified.

The safety and COVID-19 cases analyses will be censored at the date of unblinding or the receipt of an unscheduled vaccine^a, whichever event occurs first. AEs and COVID episodes reported after unblinding or receipt of an unscheduled vaccine, whichever comes first, will be listed.

The immunogenicity analyses will be censored at the date of the receipt of

- an unscheduled vaccine,
- another live vaccine,
- unknown vaccine which is received in the window of +/-29 days at each dosing,
- other not live vaccine which is received in the window of +/-15 days at each dosing.

Immunogenicity samples excluded for the above reasons will be included in the listings and flagged.

^a Unscheduled vaccine: an authorized/licensed COVID-19 vaccine offered outside of the study.

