Regimen	2	Cross Vaccination	2	Date and time of Cross Vaccination	Minimum of: a) 23:59 at the date of last contact (for early discontinuation) b) 23:59 at the date of database cut-off date in case of interim analysis c) 23:59 on Day 28 after the Cross Vaccination 1 (23:59 of day of booter vaccination + 28 days)
Follow-up 2	4			One minute after Cross Vaccination period end	Minimum of: a) 23:59 at the Date of last contact (for early discontinuation) b) 23:59 at the date of database cut-off date in case of interim analysis c) 23:59 at the Date of last visit

Note: the end date of the regimen phase should be the end date of the last post-dose period.

Adverse Events and selected other tables may display AEs (or other counts) by period. For such tables, active periods can be combined and additionally displayed. The active periods can be:

- “Post-Dose 1”
- “Post-Dose 2”
- “Post-Dose 1 and Post-Dose 2 Combined”, which refers to the “primary regimen”
- “Post- Antigen presentation or Placebo”
- “Post-Dose 1, Post-Dose 2 and Post-Antigen presentation or Placebo”, which refers to the complete regimen including Antigen presentation. It includes the 28-day period after each vaccination (dose 1, dose 2, Antigen presentation).

The primary endpoints include SAEs from the first vaccination until end of the study. This will be a combined period of post-dose 1, post-dose 1 Follow-up (FU), post-dose 2, post-dose 2 FU, post-Antigen presentation or Placebo and post-Antigen presentation or Placebo FU. This period will be labeled “Entire Period” or similar in the outputs.

The secondary endpoints include SAEs from the antigen presentation until end of the study. This will be a combined period of post-Antigen presentation or Placebo and post-Antigen presentation or Placebo FU. This period will be labeled “Entire Antigen Presentation Regimen” or similar in the outputs.

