5.3. Primary Endpoint(s) Analysis

The primary endpoints in this study, are:

Adults

Humoral Immune Response

All participants in groups 1-3 (3 dose levels of Ad26.COVS.S administered as a 2-dose schedule at a 56-day interval):

- Serological response to vaccination as measured by virus neutralization assay (VNA) titers and enzyme-linked immunosorbent assay (S-ELISA EU/mL), 28 days after Vaccination 2.
- Antibody geometric mean titers (GMTs) (VNA) and geometric mean concentrations (GMCs) (S-ELISA), 28 days after Vaccination 2.

All participants in groups 4-5 (2 dose levels of Ad26.COVS.S administered as a single vaccination):

- Serological response to vaccination as measured by VNA titers and ELISA (S-ELISA EU/mL), 28 days after Vaccination 1.
- Antibody GMTs (VNA) and GMCs (S-ELISA), 28 days after Vaccination 1.

All participants in groups 7-9 (5×10^{10} vp dose level, administered as a 2-dose schedule at a 28-day and at an 84-day interval):

- Serological response to vaccination as measured by VNA titers and ELISA (S-ELISA EU/mL), 28 days after Vaccination 2.
- Antibody GMTs (VNA) and GMCs (S-ELISA), 28 days after Vaccination 2.

Safety and reactogenicity of Ad26.COVS.S

- Solicited local and systemic AEs for 7 days after each vaccination.
- Unsolicited AEs for 28 days after each vaccination.
- Serious adverse events (SAEs) and adverse events of special interest (AESIs) throughout the study (from first vaccination until end of the study)

Adolescents

Safety and reactogenicity of Ad26.COVS.S

- Solicited local and systemic AEs for 7 days after vaccination.
- Unsolicited AEs for 28 days after vaccination.
- SAEs (incl. Multisystem Inflammatory Syndrome in Children [MIS-C]) and AESIs throughout the study (from first vaccination until end of the study).

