5.6.1. Adverse Events

5.6.1.1. Definitions

Solicited AEs shown in the tables are extracted from the investigator assessment pages (CE) of the CRF. For unsolicited AEs, only the AEs within the 28-day period following each vaccination will be presented in the safety tables except for SAEs, which will be captured and tabulated in the outputs covering the whole study period. All other collected unsolicited adverse events will be presented through listings.

Solicited administration site symptoms will be considered as related to the study vaccine (by definition).

The severity of the AEs will be classified as grade 1 to 4. Solicited events that are graded less than grade 1, are not considered as AE. In case no grades are available, the grading of the solicited events will occur according to the grading list in Appendix 3.

For AESI, the following is defined:

- Suspected AESI : as reported by investigator and presented by: Embolic and thrombotic events (SMQ) + PT; Haematopoietic thrombocytopenias (SMQ) (broad) or HLT Thrombocytopenias + PT; Other SMQ + PT.
- Suspected AESI: Embolic and thrombotic events (SMQ), Haematopoietic thrombocytopenias (SMQ) (broad) or HLT Thrombocytopenias and presented by: Embolic and thrombotic events (SMQ) + sub-SMQ1 + PT; Haematopoietic thrombocytopenias (SMQ) (broad) or HLT Thrombocytopenias + PT;
- Qualified for assessment AESI: [Embolic and thrombotic events (SMQ)] and [Haematopoietic thrombocytopenias (SMQ) (broad) or HLT Thrombocytopenias or platelet count below normal ranges per local or central laboratory report or platelet count < 150 × 10⁹/L] and presented by: Embolic and thrombotic events (SMQ) + sub-SMQ1 + PT;

^a As indicated previously, all analyses, including the safety analyses, will be conducted by actually received vaccine (“as treated” principle). The sentence “by study intervention regimens as designed per protocol” indicates that the statistical tables are designed with the planned vaccine regimens as columns. Therefore, participants who receive e.g. “Placebo, Placebo” instead of “Ad26.COV2.S 5x10¹⁰ vp, Placebo” will appear in the “Placebo, Placebo” column. However, to avoid sparse columns, participants who receive e.g. “Placebo, Ad26.COV2.S 5x10¹⁰ vp” (which is not a planned vaccine regimen) will be excluded from the statistical tables. They will be included in the listings, as well as in the programmed patient narratives where they will appear as “Subjects with vaccine misallocation”.

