6.2. Appendix 2 Changes to Protocol-Planned Analyses

In October 2020, the current study was temporarily paused because one of the pausing rules was met in study COV3001. When the pause was lifted, most of the participants in Groups 7-8 had missed their visit window for Vaccination 2, rendering the intent of the 28-day vaccination interval in these groups futile.

For safety analyses,

- the 2 subjects vaccinated before pausing rule (28-day interval) will only be shown in the listings.
- the other subjects received the vaccination 2 between 51 and 72 days after Vaccination 1. They will be integrated in the Full Analysis Set with groups 1 and 6 (56-day interval).

For immunogenicity analyses,

- subjects randomized in groups 7 and 8 won't be included in PPI set
- a modified PPI set will be defined as follows :
subjects with vaccination 2 within the window (54-64) or subjects who did not receive vaccination 2 will be integrated in groups 1 and 6
- a modified FAS set will be defined as follows :
subjects in mPPI set and subjects with vaccination 2 in (51-53) days or (65-72) days window

6.3. Appendix 3 Guidance for Industry: Toxicity Grading Scale for Healthy Adult and Adolescent Volunteers Enrolled in Preventive Vaccine Clinical Trials

The laboratory values provided in the tables below serve as guidelines and are dependent upon institutional normal parameters. Institutional normal reference ranges should be provided to demonstrate that they are appropriate.

If a laboratory value falls within the grading as specified below but also within the local laboratory normal limits, the value is considered as normal.

Serum *	Mild (Grade 1)	Moderate (Grade 2)	Severe (Grade 3)	Potentially Life Threatening (Grade 4)**
Sodium – Hyponatremia mEq/L	132 – 134	130 – 131	125 – 129	< 125
Sodium – Hypernatremia mEq/L	144 – 145	146 – 147	148 – 150	> 150
Potassium – Hyperkalemia mEq/L	5.1 – 5.2	5.3 – 5.4	5.5 – 5.6	> 5.6
Potassium – Hypokalemia mEq/L	3.5 – 3.6	3.3 – 3.4	3.1 – 3.2	< 3.1
Glucose – Hypoglycemia mg/dL	65 – 69	55 – 64	45 – 54	< 45
Glucose – Hyperglycemia Fasting – mg/dL Random – mg/dL	100 – 110 110 – 125	111 – 125 126 – 200	>125 >200	Insulin requirements or hyperosmolar coma
Blood Urea Nitrogen BUN mg/dL	23-26	27 – 31	> 31	Requires dialysis
Creatinine – mg/dL	1.5 – 1.7	1.8 – 2.0	2.1 – 2.5	> 2.5 or requires dialysis
Calcium – hypocalcemia mg/dL	8.0 – 8.4	7.5 – 7.9	7.0 – 7.4	< 7.0
Calcium – hypercalcemia mg/dL	10.5 – 11.0	11.1 – 11.5	11.6 – 12.0	> 12.0

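### SAP 4 censors safety analyses at unblinding, which conflicts with a primary SAE/AESI window that SAP 5.3, 5.1.2 and 5.6.1.1 run to the end of the study

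*SAP*

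**What the plan says.** SAP section 4 sets one rule for all safety output: "The safety and COVID-19 cases analyses will be censored at the date of unblinding or the receipt of an unscheduled vaccine", whichever comes first. Adverse events after that date are listed. A footnote defines the unscheduled vaccine, but nothing defines unblinding. The separate immunogenicity rule in the same section does not use unblinding as a trigger.

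Three other places in the SAP describe a longer window:

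- SAP 5.3 gives the adult primary endpoint as "Serious adverse events (SAEs) and adverse events of special interest (AESIs) throughout the study (from first vaccination until end of the study"). The adolescent endpoint has the same window.
- SAP 5.1.2: "The primary endpoints include SAEs from the first vaccination until end of the study". Its Entire Period runs through the follow-up after antigen presentation. For the active groups, Table 1 ends that follow-up at the last visit (Follow-up 3).
- SAP 5.6.1.1 limits unsolicited-event tables to 28 days after each vaccination, "except for SAEs, which will be captured and tabulated in the outputs covering the whole study period".

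Protocol 6.4 unblinds every adult at a visit under Amendment 5, and the 33 adolescents under Amendment 6 at about 6 months.

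On the 28-day interval, Protocol 2.1 says that this will be assessed: "Safety and immunogenicity of 28-, 56-, and 84-day vaccination intervals for the 2-dose regimen". According to the Protocol synopsis, the aim of the open-label doses offered to the placebo groups "is to recreate this 28-day vaccination interval, and to restore the objectives associated with this interval".

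**The concern.** Scheduled unblinding comes before the last visit in every group. A programmer who follows section 4 stops the SAE and AESI tables at unblinding. One who follows 5.3, 5.1.2 and 5.6.1.1 runs them to the last visit. The result is two different tables for a primary safety endpoint, with no stated order of precedence.

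The AESI part is exposed by timing. Adult AESI reporting starts at local approval of Amendment 5 (Protocol 8.3.1), and adult unblinding comes with implementation of the same amendment. Much of the prospective AESI reporting time could therefore fall after the censoring date, although the documents give no dates. The sponsor will also try to collect earlier events (Protocol 8.3.6.1).

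A second, conditional issue concerns the re-created 28-day regimen. Its doses are all given after unblinding, so under section 4 its adverse events appear only in listings. Its immunogenicity is not censored at unblinding and would be summarised as usual.

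**Working it through.** **1. Does scheduled unblinding fall inside the primary window?** Yes. Protocol 1.3.1 and Table 4 place the unblinding visit after the visit 28 days after Injection 3 and before the 6-month call. That is inside Follow-up 3 of SAP Table 1, which belongs to the Entire Period. The secondary SAE/AESI window, from antigen presentation to the end of the study, is cut at the same date.

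**2. Tabulated follow-up removed if section 4 governs.** The adult unblinding date is not given. Assumption: it lies between Injection 3 + 28 days and Injection 3 + 6 months. Nominal visit days come from Protocol 1.3.1, 1.3.3, 1.3.5 and 4.4.

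Share removed = (last visit day − unblinding day) / (last visit day − 1)

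| Group | Last visit | Unblinding day | Removed | Share |
|---|---|---|---|---|
| 1–5 | 393 | 337 | 56 of 392 | 14.3% |
| 1–5 | 393 | 197 | 196 of 392 | 50.0% |
| 9 | 421 | 365 | 56 of 420 | 13.3% |
| 9 | 421 | 225 | 196 of 420 | 46.7% |
| A, B | 337 | 169 | 168 of 336 | 50% |

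Group 7 also loses 56 to 196 days, because its later visits are counted from its actual second dose. SAP Appendix 2 places it with Group 1 for safety.

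**3. Size over the active adults.** Planned numbers are 5 × 75 + 50 + 50 = 475. Planned follow-up, with Group 7 at its nominal 364 days, is (375 × 392 + 50 × 364 + 50 × 420) / 365.25 = 510 person-years. The amount removed runs from 475 × 56 / 365.25 = 73 to 475 × 196 / 365.25 = 255 person-years, or 14% to 50%. Groups A and B have 30 planned participants (10 sentinels and 20 in the safety cohort).

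**4. What is not affected.** The 7-day and 28-day windows after doses 1, 2 and antigen presentation end by the 28-day visit after Injection 3. They therefore precede scheduled unblinding, apart from individual early unblinding.

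**5. The 28-day regimen.** Protocol 4.1 notes of Groups 7–8 that "only 2 subjects (one in each group) are vaccinated at a 28-day interval, due to a study pause", and SAP Appendix 2 says "the 2 subjects vaccinated before pausing rule (28-day interval) will only be shown in the listings". The rest of the evidence is the placebo recipients of Groups 6, 8 and 10, with a target of 3 × 25 = 75. SAP Table 1 defines Cross Vaccination 1 and 2 as regimen periods. The combinable periods in 5.1.2 and the table periods in 5.6 do not name them, and for these groups Follow-up 3 stops just before cross-vaccination.

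For scale, Protocol Table 9 gives an upper limit of 3.9% for zero events in 75. This reproduces as 1 − 0.05^(1/75) = 3.92%. That is the precision a table of 75 recipients would offer.

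**The case against.** The strongest reply is that unblinding in section 4 means individual unblinding. It is paired with receipt of an outside vaccine, which fits the individual-request procedure in Protocol 6.3. SAP 5.7.1 uses a different phrase for the trial-wide event, and Table 1 ends no phase at unblinding. This reading is possible, and under it the figures for scheduled unblinding do not arise. But it is not written, and Protocol 9.4.2 applies separate analysis from the point of unblinding to all adult data. The ambiguity itself needs resolving.

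It can also be said that a censored whole-study table is programmable, and that censoring inside a window is not automatically a contradiction. That is fair for an outside COVID-19 vaccine. It is harder to accept for an event that happens to every participant by design and cuts a window defined as reaching the end of the study.

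A reader might go further and infer that section 4 leaves the 28-day regimen with no adverse-event table. The documents do not establish this:

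- SAP 5.1.1 presents all safety results by phase, and Table 1 includes the cross-vaccination periods.
- The lists in 5.1.2 and 5.6 are worded permissively, and output detail is left to specifications that are not part of these documents.
- Lifting the censoring would not by itself name the missing periods, so the two issues are separate.
- Safety by interval rests on one sentence in Protocol 2.1; the safety objective in Protocol section 3 names dose levels and schedules, not intervals.

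Nor is listing-only a plain breach of the protocol, which leaves the details to the SAP. Listings or narratives for deaths, vaccine discontinuations due to adverse events, and severe or serious events remain (SAP 5.6.1.2). Phase counts (SAP 5.2) would allow a crude rate by hand.

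**Conclusion.** The conflict between SAP 4 and SAP 5.3, 5.1.2 and 5.6.1.1 stands and affects a primary safety endpoint. If section 4 is applied to scheduled unblinding, tabulated SAE/AESI follow-up shortens by 14–50% in Groups 1–5, 13–47% in Group 9 and about 50% in adolescent Groups A and B. These are ranges on nominal days and planned numbers, and the adult figures rest on the assumed position of the unblinding visit.

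Protocol 6.3 describes Injection 3 as given unblinded, so a reader might infer a still larger loss. The visit schedules place unblinding at least 28 days after Injection 3, so that reading is not supported. Nor does the point imply lost data: every event is still collected and listed.

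The cross-vaccination issue is secondary and conditional. If section 4 governs, events after the open-label doses are listings only. Whatever the censoring rule, the SAP should say plainly whether those periods are tabulated.

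**What to change.** In SAP 4, define unblinding. Limit censoring at unblinding to the blinded active-versus-placebo presentation, and keep censoring at an outside COVID-19 vaccine. If only individual unblinding was meant, say so.

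State that SAEs and AESIs in the originally active groups (1–5, 9, A, B, and Group 7 as integrated with Group 1) are tabulated from first vaccination to the end of the study, and also split into blinded and open-label periods.

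Add the Cross Vaccination periods of Table 1 to the table periods in SAP 5.1.2 and 5.6. For Groups 6, 8 and 10, provide solicited, unsolicited, SAE and AESI tables labelled open-label and kept apart from placebo time. For Group C (3 participants), a listing or simple count is enough.

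The cost is wording in three SAP sections and a few extra tables on phases already defined, with no new data. The drawback is that some tables will contain events reported without blinding, which the period split and labels make visible.

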- 6 Participant has a history of chronic urticaria (recurrent hives), eczema or adult atopic dermatitis.
- Participant received treatment with immunoglobulins in the 3 months or blood products in the 4 months before the planned administration of the first dose of study vaccine or has any plans to receive such treatment during the study.
- 8 Participant received or plans to receive:
 - c. Licensed live attenuated vaccines within 28 days before or after planned administration of the first or subsequent study vaccinations.
 - d. Other licensed (not live) vaccines within 14 days before or after planned administration of the first or subsequent study vaccinations.

- 9 Criterion modified per Amendment 1:
 - 9.1 Criterion modified per Amendment 2:
 - 9.2 Criterion modified per Amendment 3:
 - 9.3 Participant received an investigational drug (including investigational drugs for prophylaxis of COVID-19) or used an invasive investigational medical device within 30 days or received investigational Ig or monoclonal antibodies within 3 months, or received convalescent serum for COVID-19 treatment within 4 months or received an investigational vaccine (including investigational Adenoviral-vectored vaccines) within 6 months before the planned administration of the first dose of study vaccine or is currently enrolled or plans to participate in another investigational study during the course of this study.

Note: Participation in an observational clinical study is allowed at the investigator's discretion; please notify the sponsor (or medical monitor) of this decision.

Efforts will be made to ensure inclusion of participants who have not been previously enrolled in coronavirus studies and to prevent participants from subsequently enrolling in other coronavirus studies during their participation in this study.

The use of any coronavirus vaccine (licensed or investigational) other than Ad26.COV2.S is disallowed at any time prior to vaccination (see also Exclusion Criterion 19) and during the study except under the conditions described in Section 6.7.

- 10 Criterion modified per Amendment 1:
 - 10.1 Participant is a woman who is pregnant, breastfeeding, or planning to become pregnant within 3 months after the last dose of study vaccine.

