6.9. Prestudy and Concomitant Therapy

Prestudy specific therapies such as analgesic/antipyretic medications and non-steroidal anti-inflammatory drugs, corticosteroids, antihistamines, and vaccinations administered up to 30 days before the first dose of study vaccine must be recorded at screening.

Concomitant therapies such as analgesic/antipyretic medications and non-steroidal anti-inflammatory drugs, corticosteroids, antihistamines, and vaccinations must be recorded from the first dose of study vaccine until 28 days after administration of study vaccine, and thereafter, pre-dose on the day of vaccination and for 28 days after the subsequent dose of study vaccine. All other concomitant therapies should also be recorded if administered in conjunction with a confirmed COVID-19 case or with new or worsening AEs or suspected AESIs reported per protocol requirements outlined in Section 8.3.1.

Use of any experimental medication (including experimental vaccines other than the study vaccine) will lead to discontinuation of administration of any subsequent study vaccination. Any participant who has been given an anti-COVID-19 vaccine (other than study vaccine) or treatment will not receive further study vaccination. Participants may not receive an investigational drug (including investigational drugs for prophylaxis of COVID-19) or use an invasive investigational medical device within 30 days or receive an investigational Ig or monoclonal antibodies within 3 months, or receive convalescent serum for COVID-19 treatment within 4 months or receive an investigational vaccine (including investigational Adenoviral-vectored vaccines) within 6 months before the planned administration of the first dose of study vaccine.

Licensed live attenuated vaccines should be given at least 28 days before or at least 28 days after a study vaccination. Other licensed (not live) vaccines (eg, tetanus, hepatitis A, hepatitis B, rabies) should be given at least 14 days before or at least 14 days after administration of study vaccine in order to avoid potential confusion of adverse reactions and potential immune interference. The use of any coronavirus vaccine (licensed or investigational) other than Ad26.COV2.S is disallowed at any time prior to vaccination and during the study. If a vaccine is indicated in a post-exposure setting (eg, rabies or tetanus), it must take priority over the study vaccine.

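### SAP 4 censors immunogenicity after a live non-study vaccine with no time window, although the protocol permits live vaccines outside a 28-day washout

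*SAP*

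**What the plan says.** SAP section 4 (Populations) sets the rule: "The immunogenicity analyses will be censored at the date of the receipt of" any of four kinds of vaccine. The first is a COVID-19 vaccine obtained outside the study. The second is "another live vaccine", with nothing after it. The third is "unknown vaccine which is received in the window of +/-29 days at each dosing" and the fourth is "other not live vaccine which is received in the window of +/-15 days at each dosing". Samples removed in this way stay in the listings with a flag.

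The protocol states the washouts twice, in different words:

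- Section 6.9, live: "Licensed live attenuated vaccines should be given at least 28 days before or at least 28 days after a study vaccination". Section 6.9, not live: such vaccines "should be given at least 14 days before or at least 14 days after administration of study vaccine".
- Exclusion criterion 8 for adults (5.2.1), live: "Licensed live attenuated vaccines within 28 days before or after planned administration of the first or subsequent study vaccinations". Not live: "Other licensed (not live) vaccines within 14 days before or after planned administration of the first or subsequent study vaccinations".

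Protocol 6.9 ties removal from the immunogenicity analyses to receipt of a prohibited medication, depending on when it was taken. SAP Appendix 2, which lists changes to the protocol-planned analyses, does not mention non-study vaccines.

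**The concern.** The protocol treats a live vaccine outside the 28-day washout as permitted. The SAP bullet for live vaccines makes no such distinction. A programmer who follows the text would censor a participant who complied with the protocol, and the censoring would run from that date to the end of follow-up. The rule is written for the immunogenicity analyses in general and not for the per-protocol set alone, so the full-analysis-set results are not stated to be spared.

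The two bullets that do carry a window use 15 and 29 days where the protocol uses 14 and 28. That raises a smaller question: whether vaccines given on days the protocol permits can also trigger censoring. What is at stake is the number of samples behind the later time points, and a rule that two programmers could apply differently.

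**Working it through.** **Inputs** (nominal schedule, visit windows ignored):

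- Groups 1-5 (Schedule of Activities 1.3.1): study injections on Days 1, 57 and 169; humoral samples on Days 1, 15, 29, 57, 64, 71, 85, 169, 176, 197 and 393, which is 11.
- Group 9 (Schedule 1.3.3): injections on Days 1, 85 and 197; humoral samples on Days 1, 85, 92, 99, 113, 197, 204, 225 and 421, which is 9.
- Washouts: 28 days (live) and 14 days (not live).

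**1. Days on which a live vaccine is permitted.** Under 6.9, day t is permitted if |t − d| ≥ 28 for every injection day d. In Groups 1-5:

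- Day 29 (1 + 28 = 29 and 57 − 28 = 29): 1 day.
- Days 85 to 141 (57 + 28 = 85 and 169 − 28 = 141): 57 days.
- Days 197 to 393 (169 + 28 = 197): 197 days.

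The total is 1 + 57 + 197 = 255 of 393 days. If exclusion 8 is read inclusively (|t − d| > 28), Days 86-140 and 198-393 remain: 55 + 196 = 251. The SAP bullet censors on every one of these days. Had the live bullet carried the 29-day window of its neighbour, read inclusively, Days 87-139 (53) and 199-393 (195) would not trigger censoring. That spares 248 of the 255.

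**2. What one such vaccine removes.** A live vaccine on Day 120 is 120 − 57 = 63 days after the second injection and 169 − 120 = 49 days before the third, so it is permitted under both wordings. The later samples are Days 169, 176, 197 and 393: 4 of 11. Day 176 is the secondary endpoint, 7 days after antigen presentation.

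In Groups 1-3 the primary Day 85 sample is hardly exposed. The only permitted live-vaccine day between the first injection and Day 85 is Day 29, a boundary day that exclusion 8 bars if read inclusively. Group 9 has more room. A live vaccine on Day 43 is 43 − 1 = 42 days after the first injection and 85 − 43 = 42 days before the second. It removes 8 of 9 samples, including the primary Day 113 sample.

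**3. The 15- and 29-day limits.** Let k = vaccine date minus dose date. The table shows the offsets that the protocol permits and the SAP censors for a not-live vaccine.

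| Reading of the SAP's 15 days | Against 6.9 (at least 14) | Against exclusion 8 (within 14, inclusive) |
|---|---|---|
| Offset, inclusive | −15, −14, +14, +15 | −15, +15 |
| Offset, strictly under 15 | −14, +14 | none |
| Relative day | −15, −14, +14 | −15 |

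The relative-day row applies the SAP 5.1.1 convention to each dose, which is an assumption. That convention adds 1 on or after the reference day and nothing before it. Relative day +15 is therefore 14 days after dosing, while −15 is 15 days before. The same pattern holds at 28 and 29 days for an unknown vaccine set against the live washout. The protocol has no unknown category, so that comparison is also an assumption.

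An excess that is clear under both protocol wordings is thus k = −15 (or −29) on two of the three readings, and k = +15 (or +29) on one. If k = −15 falls before the first dose, the receipt date precedes Day 1 and all 11 Group 1-5 samples are censored. Section 6.9 requires vaccines in the 30 days before the first dose to be recorded, so such a case would be seen.

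**The case against.** The strongest reply on live vaccines is that the missing window is a drafting slip. The 29-day window for unknown vaccines looks like the live washout, so the two were probably meant to share it. That is plausible, but the SAP does not say it.

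A second reply concerns capture. Section 6.9 and the concomitant-medication footnote to Schedule 1.3.1 require vaccinations to be recorded only up to 28 days after a dose, and again from the next dosing day. After the second injection that means up to Day 57 + 28 = 85, then from Day 169. A Day 120 live vaccine need not be recorded unless it accompanies an adverse event or a COVID-19 case. Yet the Schedule row for concomitant medication is marked continuous. Capture is therefore possible but not assured. This lowers the expected number affected, and it also means that an unlimited rule would bite according to what each site happened to record.

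On the 15 and 29 days, the day-counting defence largely stands. If these are relative days, the post-dose limits coincide with an inclusive reading of exclusion 8. A reader might infer that the SAP plainly uses wider washouts than the protocol, so that a not-live vaccine on Day 16 is certainly censored. The documents do not support that: Day 16 is 15 days after the first dose and is censored only if 15 is an inclusive offset. Nor do they support the idea that vaccination dates will cluster on the boundary days.

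**Conclusion.** The point holds for live vaccines on the text alone, whatever day-counting convention is used. The bullet has no window and the protocol permits live vaccines outside 28 days. For the not-live and unknown bullets the finding is a possible excess of about one day per side, clearest before dosing, and it depends on how the limits are read.

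The effect is probably very small. The documents give no count of affected participants. As an assumption only, if 0 to 3% of a 75-participant group had such a vaccine, that would be 0 to 0.03 × 75 = 2.25, so about 0 to 2 people. The study is descriptive with no formal hypothesis test, so no decision rule is at risk. A reader might also infer that data are thrown away. They are not: samples before the vaccine stay in the analyses, and later ones are listed and flagged.

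**What to change.** In SAP 4, attach to the live-vaccine bullet a window around each dosing that matches the protocol's live-vaccine washout, so that only a vaccine breaching the washout triggers censoring. State whether the 15- and 29-day limits are relative days or offsets, and whether they are inclusive, so that no vaccine permitted by the protocol triggers censoring. If a wider limit is intended, say so and give the reason in Appendix 2.

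Section 6.9 and exclusion 8 disagree on whether days 14 and 28 themselves are allowed. The SAP derivation must reconcile them and state the treatment of those days; which wording governs is for the sponsor to settle.

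The cost is a wording change and one derivation rule. No new data are needed. No protocol amendment is needed either, and rewriting exclusion 8 would gain little now that enrolment has ended. The downside is that a few boundary-day samples stay in the analysis.
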